### **6.3.2. Exploratory Efficacy**

All exploratory efficacy endpoints will be summarized by the treatment group at each scheduled visit. Descriptive statistics for continuous variables consists of mean, standard deviation (SD), median, minimum, and maximum. For categorical variables, numbers and percentages will be summarized.

Additional analysis may be performed as appropriate for the following exploratory efficacy endpoints.

#### Clinical Cure

Clinical cure is defined as having all signs and symptoms completely resolved, including inflammatory/non-inflammatory lesions and pruritus.

The number and percent of subjects who exhibit clinical cure (Yes or No) at Day 28 will be presented by treatment group. A Cochran-Mantel-Haenszel test adjusted by study site stratification will be performed to compare the complete cure rates between the two treatment groups upon the same data imputation approach defined for primary endpoint.

This analysis can be performed on the I-ITT population on both OC and LOCF data as needed.

#### Microscopic Cure

Microscopic cure is defined as microscopic or dermatoscopic demonstration of the absence of mites, eggs, and/or scybala, and negative for burrows.

The number and percent of subjects who exhibit microscopic cure (Yes or No) at Day 28 will be presented by treatment group. A Cochran-Mantel-Haenszel general association test stratified by study site will be used to compare the two treatment groups upon the same data imputation approach defined for primary endpoint.

Additional analyses can be performed on the I-ITT population by applying a logistic regression model adjusted for baseline factors if there is necessity to further analyze this component of the complete cure.

CMH analysis can be performed on the I-ITT population on both OC and LOCF data as needed.

#### Number of New Lesions

The number of new lesions at Day 28 will be analyzed using a negative binomial regression model to compare the treatment difference. The model will include treatment

group and study site (small sites pooled) as fixed factors, and baseline total lesion count as a covariate.

This analysis will be performed on the I-ITT population using LOCF approach.

#### Total Lesion Counts

Total lesion counts will be calculated as the sum of pre-existing lesions and new lesions. The baseline captures the total lesions on the day of first study drug administration.

The change from baseline to Day 28 will be analyzed using an analysis of covariance (ANCOVA) model with treatment and study site (small sites pooled) as factors and baseline total lesion counts as a covariate.

This analysis will be performed on the I-ITT population using LOCF approach. In addition, descriptive statistics will be provided by visit based on OC data.

#### Subset in ITT - subjects who were infested at baseline

A subset of subjects in ITT population who were infested at baseline will be summarized to display the proportion of the completely cured subjects.

The same analyses described for primary analysis will be performed for this subset of subjects using the similar data imputation approach described for primary analysis.

### **6.4. Safety Analyses**

#### **6.4.1. Adverse Events**

Adverse events will be coded using Medical Dictionary for Regulatory Activities (MedDRA) and summarized by System Organ Class (SOC) and Preferred Term (PT) for each treatment group. All AEs will be captured throughout the study period from the enrollment to the final visit (Visit 3) or the ET visit. AEs that occur after the first dose of study treatment will be considered as treatment-emergent adverse events (TEAE). Within each SOC or PT, subjects will be counted only once if they had one or more than one event reported during the treatment period (the subject is counted for the event with the maximum severity).

Adverse events will be summarized by presenting:

- the number and percentage of subjects experiencing any TEAE
- the number and percentage of subjects experiencing any TEAE grouped by SOC and PT

- the number and percentage of subjects experiencing any Serious Adverse Events (SAEs)
- the number and percentage of subjects experiencing any TEAE grouped by SOC and PT and maximum severity
- the number and percentage of subjects experiencing any TEAE grouped by SOC and PT and maximum relationship to IP
- the number and percentage of subjects experiencing any TEAE leading to study medication discontinuation.
- The number and percentages of subjects experiencing any unexpected life-threatening adverse reaction

A listing will be produced for all subjects who reported SAEs or who discontinued study medication due to TEAEs.

All AEs (ie, pretreatment AEs and TEAEs) will be listed by subject. However, only TEAEs will be included in the summary tables.

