#### **4.3 Subject Withdrawal Criteria**

Subjects may be removed from the study for reasons including the following:

1. Significant protocol violation on the part of the Investigator or subject.

2. Significant noncompliance on the part of the subject as determined by the Investigator in consultation with the Medical Monitor.
3. Subject withdrawal of consent.
4. During the study, subject has the need for medications, supplements, or other products that are excluded (see Section 7.4, “Prohibited Medications”).
5. Occurrence of any AE or condition that could, in the Investigator’s opinion, interfere with the evaluation of the treatment effect or put the subject at undue risk.

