**6.7 Early Termination Procedures**

The term "Early Termination" refers to a subject's non-completion of a study whether by his or her own choice or the investigator's decision or due to discontinuation of the study by ParaPRO LLC. In the absence of a medical contraindication or significant protocol violation, every effort will be made by the Investigator to keep the subject in the study. Should the subject decide to withdraw, an early termination visit should be conducted, which will include all procedures

normally done at Visit 3. The ET subject will not be dispensed 5% Permethrin and the PI will refer the subject to their primary care physician for follow-up.

The primary reason for a subject withdrawing prematurely should be selected from the following categories:

***Adverse Event or Serious Adverse Event***—events that are associated with discontinuation.

***Noncompliance with protocol***—the subject failed to adhere to the protocol requirements. The deviation necessitated premature termination from the study.

***Withdrawal of Consent***—subject desires to withdraw from further participation in the study in the absence of an adverse event or a medical need to withdraw.

***Lost to Follow-up***—the subject did not return for one or more follow-up visit(s) following dispensing of test drug. The reason was unknown and appropriate due diligence was exerted by the investigator to contact the subject and encourage their return.

***Other***—causes of premature termination from the study other than the above, such as theft or loss of IP, termination of study by ParaPRO LLC, etc. The details of the premature termination in this “other” category should be documented fully.

The investigator should notify Concentrics Research promptly when a subject is withdrawn, or if the study is stopped at his/her site by the IRB or if the investigator elects to stop the study.

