### **9.5 Action Taken and Outcome**

The Action Taken with IP for every AE will be reported as Dose Not Changed or Dose Withdrawn. The Outcome of each AE will be entered as either: Recovered/Resolved, Recovered/Resolved with Sequelae, Not Recovered/Not Resolved, Fatal, or Unknown.

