### 2.2. Trial Design and Visit Structure

The primary study is a double blind, two-arm, 28-day, placebo-controlled study enrolling approximately 120 infested “index” subjects enrolled and randomized 1:1 to Natroba™ or Placebo in order to achieve, with attrition, 96 subjects completed in the study.

All members of a household (no more than 6 individuals) with a suspected “index” subject must be screened at the first visit. In this study, “index” subjects are defined as the youngest infested household member ( $\geq 4$  years). If the household has at least one member with active scabies infestation and meet all other criteria, they must all agree to participate in the study. Household members who do not present with scabies at the screening visit must also agree to apply the same blinded investigational product (IP) as household members who present with scabies (see Table 6-1 Schedule of Procedures in the protocol

for status assessment). All household members must agree to participate in the study or none will be enrolled.

After screening on Day 1, all randomized subjects will be dispensed IP (Natroba™ or Placebo) to apply at home later the same day. IP will be applied as a single treatment over the entire body from the neck down to the toes (including the soles of the feet) and to the scalp (if balding) or hairline, temples and forehead on the same day. Subjects less than 12 years of age should be assisted with administration by a parent, guardian or caregiver. Subjects will rub the treatment into the skin followed by a 10-minute wait period before getting dressed. Showering or bathing must not occur earlier than 6 hours after treatment and no later than at least 1 hour prior to Day 2 visit.

On Day 2 (Visit 2), all household members will return for general skin and eye assessments of possible irritation, and to confirm that all IP was left on for a minimum of 6 hours before bathing or showering. If a subject reports an adverse event assessed as related by the principal investigator (PI) on Day 2 (Visit 2) then a follow-up visit with the investigator must be scheduled within 7 days of visit. All household members will receive a well-being phone call on Day 14 to continue to emphasize instructions to prevent re-infestation, determine if any concomitant medications have been used, and check for adverse events

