## **6.2. Subject Characteristics**

### **6.2.1. Subject Disposition and Deviations**

The tabulation of number of subjects in each treatment group and overall will be displayed for all subjects who are screened, randomized, and in each analysis population.

The number and percent of subjects who completed or discontinued the study will be displayed for each treatment group and overall together with reasons for early termination, where the percent is with respect to the total number of randomized subjects in that treatment group.

Protocol deviations will be listed.

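### With a single Day 1 application, the summary of TEAEs leading to study medication discontinuation will be near zero by construction, and no AE table or special listing identifies which TEAE led to withdrawal from the study

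*SAP*

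**What the plan says.** **Treatment.** SAP 2.2 states that "IP will be applied as a single treatment over the entire body from the neck down to the toes". Protocol 5.5 and 7.8 have IP stay on for at least 6 hours and be washed off at least 1 hour before Visit 2, on Day 2. Under SAP 6.4.1 a TEAE starts after the first dose, which here is the only dose.

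**AE summaries.** SAP 6.4.1 includes "the number and percentage of subjects experiencing any TEAE leading to study medication discontinuation", and Protocol 8.5.4 has the same row. The special listing follows the same criterion: "A listing will be produced for all subjects who reported SAEs or who discontinued study medication due to TEAEs".

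**AE record.** Protocol 9.5 offers two action codes: "The Action Taken with IP for every AE will be reported as Dose Not Changed or Dose Withdrawn". Its outcome codes run from recovered to fatal or unknown, and none means that the subject left the study.

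**Leaving the study.** Protocol 4.3 allows removal for an AE that could "interfere with the evaluation of the treatment effect or put the subject at undue risk". Protocol 6.7 makes adverse event or serious adverse event a category of primary reason for early termination, described as "events that are associated with discontinuation". SAP 6.2.1 tabulates completions and discontinuations by arm "together with reasons for early termination, where the percent is with respect to the total number of randomized subjects in that treatment group".

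**The concern.** The row and listing are worded for a trial with continued dosing, where stopping the drug because of an AE is a standard measure of tolerability. Here dosing is over before the first visit at which AEs are collected. What can still happen because of an AE is that the subject leaves the study, and the AE summaries have no row for that.

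The primary objective covers safety as well as efficacy, so the AE section of the report should be able to say which events led subjects to withdraw, how severe they were, and whether they were judged related. As planned, the one AE row on discontinuation answers a question that can hardly arise, and the question that can arise is not answered at event level.

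**Working it through.** The plan gives no figure on this point, so the check is to follow an AE through the planned outputs according to when it occurs. The inputs are the single application (SAP 2.2), the wear time and wash-off (Protocol 5.5, 7.8), AE collection on Days 2, 14 and 28/ET (SAP 3.1), the AE form items (Protocol 9.2 to 9.5), the AE outputs (SAP 6.4.1) and disposition (SAP 6.2.1).

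| Event | Medication left to stop? | Discontinuation row | Special listing | Where else it appears |
|---|---|---|---|---|
| Before wash-off, cuts application or wear time short | Yes, in the sense of shortened exposure | Could count | Could appear | TEAE tables, all-AE listing, compliance listing |
| After wash-off, non-serious, subject withdraws | No | Not counted | Absent | TEAE tables, all-AE listing, disposition under the AE reason |
| After wash-off, serious, subject withdraws | No | Not counted | Present as an SAE, not marked as the cause of withdrawal | TEAE and SAE tables, all-AE listing, disposition under the AE reason |

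**Step 1: the row.** Only the first line can contribute. From Visit 2 to Day 28, which is nearly all of follow-up, the numerator cannot increase. The denominator is the safety population, assumed in SAP 5.1 to be about 360 (120 index + 240 non-index). The expected result is therefore near 0 of about 360, and it does not depend on how many subjects withdraw because of AEs.

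**Step 2: the record.** Take an AE that ends participation after wash-off. The site has two action codes. The literal choice is that the dose was not changed, which leaves the row empty. The other code would record something that did not happen, and use of it would differ between sites. Neither says that the subject left because of this event. The SAP does not name the field from which the row is derived, so nothing there resolves this.

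**Step 3: recovering the link from other outputs.** Protocol 9.2 requires a description, dates, severity, relationship, action, outcome and seriousness for each AE. The termination reason in Protocol 6.7 is one primary category per subject and names no event. If a withdrawn subject had a single AE, matching the listings by subject number suggests the cause. If the subject had several, no described field says which one it was.

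**Step 4: denominators.** Disposition percentages use randomized subjects (SAP 6.2.1, Protocol 8.5.1), while safety analyses use treated subjects (Protocol 8.3). The disposition count is therefore not a like-for-like replacement for an AE row.

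**The case against.** The strongest reply is that a reader might infer that AEs causing withdrawal are missed, and that this is not so. The documents bear the reply out:

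- Such an AE is still a TEAE. It counts in the overall, SOC/PT, severity and relationship tables of SAP 6.4.1.
- All AEs are listed by subject, and SAP 6.1.1 puts all subject data in listings, including data that appear in no table.
- Subjects whose primary reason is an AE are counted by arm in disposition.
- Protocol 9.1 gives events that resulted in leaving the study as examples of what should be recorded as AEs.

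It can also be said that the row has some content, because a reaction during the wear time could qualify, and that application and removal of IP are already listed by subject (SAP 6.2.2). Both are right. They make the row nearly empty rather than void, and they make a separate count of early wash-off optional.

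A reader might also infer that a zero row would mislead about tolerability. That goes too far: the zero would be literally true, and the disposition table would show AE withdrawals alongside it.

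What remains is narrow. No AE table or special listing identifies the TEAE that led to withdrawal, and the AE form as described has no field for it.

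**Conclusion.** The point holds as a minor reporting gap. The discontinuation row and the matching half of the special listing will be near zero by construction in both arms. The events themselves are collected, tabulated and listed, and withdrawals for AEs are counted by arm. What is missing is the identification of the event behind each such withdrawal.

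The number of subjects affected cannot be given. The documents allow for dropout of at most 20% but do not say what share would be due to AEs. The conclusion does not need that share, because the row stays near zero at any value of it.

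No hypothesis test, analysis population or endpoint definition changes. The conclusion rests on two readings: that stopping study medication means stopping the IP, as the Protocol 9.5 codes imply, and that the AE form holds only the items described in Protocol 9.2 to 9.5. If the eCRF already has a field marking the AE that led to withdrawal, only the wording of the row and listing needs to change.

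**What to change.** - In SAP 6.4.1 and Protocol 8.5.4, reword the row to TEAE leading to withdrawal from the study, by treatment group on the safety population, showing SOC and preferred term, severity and relationship.
- Reword the special listing to subjects with an SAE or with a TEAE leading to withdrawal from the study.
- Add one flag to the AE form for the event that led to withdrawal, linked to the early-termination reason in Protocol 6.7 and checked for agreement with it before database lock. Describe it in Protocol 9.5 beside the existing action codes.
- Optionally, report separately any TEAE that led to incomplete application or early wash-off, so that the content of the present row is kept.

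The cost is one table and one listing redefined and one eCRF field. No visits or assessments are added.

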#### **6.4.2. General Skin and Eye Irritation Assessments**

Skin and eye irritation will be captured as adverse events, as defined in Section 9.1 of the protocol. Eye irritation assessment ratings will be summarized descriptively for each treatment group by visit.

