## PROTOCOL SYNOPSIS

|  |                               |
|--|-------------------------------|
| TITLE:
A Phase 3, Randomized, Double Blind, Placebo-Controlled Study to Assess the Safety and Efficacy of Natroba™ (spinosad) for the Treatment of Scabies   |                               |
| PROTOCOL NUMBER:
SPN-304-15  |                               |
| INVESTIGATIONAL PRODUCT:
Natroba™ (spinosad) Topical Suspension, 0.9%  | U.S. IND No.
66,657 |
| PHASE:
3   |                               |
| INDICATION:
Treatment of scabies   |                               |
| OBJECTIVES:
The primary objective is to assess the safety and efficacy of topical Natroba™ (spinosad) versus Placebo for the complete cure of scabies after a single treatment.  |                               |
| ENDPOINTS:
The primary efficacy endpoint is the proportion of “index” subjects completely cured of scabies by Day 28. The “index” subject is defined as the youngest infested household member (≥4 years). Complete cure is defined as demonstration of both clinical cure (all signs and symptoms have completely resolved, including burrows, inflammatory/non-inflammatory lesions and pruritus) and microscopic or dermatoscopic cure demonstrating the absence of mites, eggs, and/or scybala, and negative dermatoscopy for burrows.

Safety endpoints include the evaluation of adverse events, general skin and eye irritation, clinical laboratory assessments, vital signs, and use of prior and concomitant medications.  |                               |
| POPULATION:
Approximately 360 subjects will be enrolled in the study. The approximate 360 total is based on: 120 households, each with an “index” subject and approximately 2 additional subjects per household (infested or not) for 360 total. The 120 “index” subjects with confirmed scabies infestation will comprise the primary efficacy population in order to achieve, with attrition, 48 subjects completed per treatment group (Natroba™ versus Placebo). In this study, “index” subjects will be defined as the youngest infested household member (≥4 years). All household members of the “index” subject will be randomized to the same treatment.  |                               |

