**SAFETY ASSESSMENTS:**

Safety assessments include monitoring of AEs on study Days 1, 2, 14 (phone call) and 28, general skin and eye irritation assessments on Days 1, 2 and 28, vital signs on Days 1 and 28, laboratory assessments on Days 1 and 28, prior medications on Day 1 and concomitant medications on Days 2 and Day 28. For early termination (ET), the Day 28 procedures will also be completed.

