## 5 STUDY TREATMENTS

### 5.1 Identity of Investigational Products

The IPs for the study are Natroba™ (spinosad) Topical Suspension (0.9%) and Placebo control. Both of the IPs will be manufactured by Ei LLC, Kannapolis, NC and provided by ParaPRO LLC, Carmel, IN.

Clinical packaging will be a 4-oz. High Density Polyethylene (HDPE) bottle with an orifice reducing plug and a screw on cap with liner.

Natroba™ Topical Suspension contains 9 mg spinosad per gram in a viscous, slightly opaque, light orange colored vehicle consisting of water, isopropyl alcohol, benzyl alcohol, hexylene glycol, propylene glycol, cetearyl alcohol, stearylalkonium chloride, cetareth-20, hydroxyethyl cellulose, butylated hydroxytoluene, FD&C Yellow #6. The vehicle (Placebo) lacks spinosad.

The methods used in, and the facilities and controls used for the manufacturing, processing, packaging, and holding of this drug substance conform with Current Good Manufacturing Practices (cGMP) in accordance with 21 CFR Parts 210 and 211. ParaPRO LLC will maintain certificates of analysis for each ingredient, documenting its purity and potency, and will provide Concentrics Research with Certificates of Analysis for both test and control products.

The following will be printed on the product label (Appendix 1):

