#### General Skin and Eye Irritation Assessments

Skin and eye irritation will be captured as adverse events, as defined in Section 9.1. Eye irritation assessment ratings will be summarized descriptively for each treatment group by visit.

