## 9 ADVERSE EVENT MONITORING

### 9.1 Definition

An AE is defined as any untoward medical occurrence in a subject or clinical investigation (vital signs, physical change, etc.) following the subject's first dose of IP that does not necessarily have a causal relationship with this treatment. An AE can be any unfavorable or unintended sign (including an abnormal finding on vital signs, physical change, etc.), symptom, or disease temporally associated with the use of an IP, whether or not related to the IP.

This includes any adverse occurrence that is new in onset or aggravated in severity, duration or frequency from the baseline condition (including the physical examination), or abnormal results of diagnostic procedures (including vital sign abnormalities).

Examples of untoward medical events that should be considered AEs are those that:

- resulted in discontinuation from the study,
- required treatment or any other therapeutic intervention,
- required further diagnostic evaluation (excluding a repetition of the same procedure to confirm the abnormality),
- are associated with clinical signs or symptoms judged by the Investigator to have a significant clinical impact.

Examples of what an AE is not:

- A surgical procedure
- A situation where an untoward event did not occur, (e.g. a social hospitalization)
- The disease being studied, unless progression is more severe than anticipated
- Lack of efficacy
- Baseline conditions that have not worsened in severity or frequency
- Abnormal findings or test results (unless considered clinically significant in the opinion of the investigator or specifically defined elsewhere in the protocol) related to the disease being studied (unless more severe than expected).

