### **3.2. General Skin and Eye Assessments**

On Day 1, the skin will be assessed to determine eligibility – no evidence of crusted scabies, normal skin in non-infested areas. On Days 1 and 2, the skin and eye assessments will include documentation of presence or absence of irritation, and verbal verification that the treatment topical suspension remained on for at least 6 hours before being washed off. On Day 28/ET, skin and eye assessments will include evidence of irritation.

Eye irritation will be rated:

- 0 no irritation
- 1 mild scleral, lid, and/or conjunctiva injection
- 2 moderate scleral and or lid injection with conjunctival erythema
- 3 severe scleral and/or lid injection with conjunctival erythema and purulent drainage

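### Skin irritation, a named safety endpoint, has no post-baseline summary of its own: the plan tabulates it only through adverse event reporting, where irritation in infested skin can be classed as scabies

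*SAP*

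**What the plan says.** The endpoint list in the protocol synopsis separates skin irritation from adverse events: "Safety endpoints include the evaluation of adverse events, general skin and eye irritation". The synopsis safety section schedules "general skin and eye irritation assessments on Days 1, 2 and 28".

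SAP 3.2 defines what is recorded: "On Days 1 and 2, the skin and eye assessments will include documentation of presence or absence of irritation". Protocol 7.7 says the same, and both documents add an assessment for evidence of irritation on Day 28 or early termination. Eye irritation has a 0 to 3 scale. Skin irritation has no grade.

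For analysis, SAP 6.4.2 states: "Skin and eye irritation will be captured as adverse events, as defined in Section 9.1 of the protocol". Protocol 8.5.4 has the matching sentence. Both sections then add a summary for the eye alone: "Eye irritation assessment ratings will be summarized descriptively for each treatment group by visit".

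Protocol 9.1 defines an adverse event to include anything new in onset or aggravated from the baseline condition. Its examples of what is not an adverse event include "The disease being studied, unless progression is more severe than anticipated" and "Baseline conditions that have not worsened in severity or frequency".

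**The concern.** The product is applied over nearly the whole body of people whose skin is, by the entry criteria, already affected in at least one household member. Protocol 1.1 describes scabies as intense itching with a pimple-like rash, and Protocol 7.3 warns that severe pruritus is common. On Day 2, redness or itching in an infested area could be the application or the disease. If the investigator judges it to be the disease, the exclusions in Protocol 9.1 allow it to stay out of the adverse event record, and so out of every post-baseline table.

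At stake is the report of local tolerability after a single application. Day 2 is the scheduled skin reading closest to application and wash-off. As written, the plan produces no by-arm figure for how many subjects had skin irritation that day. What reaches a table depends on attribution by investigators at approximately 5 to 10 sites. The primary efficacy analysis is not touched.

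**Working it through.** There is no figure in the plan to reproduce. The documents give neither an irritation rate nor a rate at which irritation would be attributed to scabies, so the check compares the text.

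**Step 1. Is there a by-visit skin table anywhere?** The safety measures compare as follows:

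- Eye irritation (SAP 6.4.2): adverse event capture plus a descriptive summary by visit and arm.
- Vital signs (SAP 6.4.4): observed values and change from baseline by visit and arm.
- Laboratory results (SAP 6.4.3): observed values and change by visit and arm, plus shift tables.
- Skin irritation (SAP 6.4.2): adverse event capture only.

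**Step 2. Does another provision fill the gap?** Three come close:

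- SAP 6.1.1 promises listings of all subject data. A listing shows each Day 2 result but gives no count or percentage by arm.
- SAP 6.2.3 includes the SAP Section 3 safety scores among the baseline summaries. That can cover Day 1, not Days 2 and 28.
- The synopsis, under statistical analyses, promises descriptive changes from baseline to Day 28 for applicable parameters. Skin is not named, Day 2 is skipped, and the SAP safety section does not carry the promise over to skin.

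None of these yields a Day 2 result by arm.

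**Step 3. What does the adverse event route capture?** Protocol 9.1 sorts the possible findings as follows:

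- Irritation absent on Day 1 and present on Day 2, attributed to the application: an adverse event.
- Irritation present on Day 1 and judged worse on Day 2: an adverse event as an aggravated finding, with severity graded under Protocol 9.3. The present/absent skin item alone cannot show this worsening.
- Irritation present on Day 1 and unchanged: not an adverse event, as is usual for a treatment-emergent count.
- Irritation in infested skin that the investigator attributes to scabies: not an adverse event unless progression exceeds what was anticipated.

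The last group is the open one. A further exclusion covers abnormal findings related to the studied disease, with exceptions for findings that are clinically significant, defined elsewhere in the protocol, or more severe than expected.

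**Step 4. Is the capture rule itself clear?** The sentence in SAP 6.4.2 and Protocol 8.5.4 can be read in two ways: every observed irritation becomes an adverse event, or irritation becomes one only if it passes the Protocol 9.1 definition. The documents do not say which governs, so two sites could code the same finding differently.

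**Step 5. Who is affected?** SAP 5.1 expects about 360 subjects in the safety population: 120 index and 240 non-index. Every index subject is infested; non-index members may or may not be. Inclusion criterion 4 requires normal-appearing skin in noninfested areas, so the attribution problem centres on infested areas. Members without scabies at baseline receive the same product, and irritation in them is least likely to be confused with the disease. No safety table separates them, although SAP 6.3.2 analyses the infested subset for efficacy.

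**The case against.** The strongest reply is that Protocol 9.1 already does the work. New or aggravated irritation is an adverse event, dropping unworsened baseline findings is normal practice, and the disease exclusion is conditional. The adverse event route also grades severity, which the present/absent item does not. Adverse events are collected at the Day 2 visit, and one judged related leads to an investigator visit within 7 days. The eye and skin sections may differ simply because only the eye has ratings to summarise.

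Most of this stands, and it rules out several stronger readings:

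- A reader might infer that irritation will necessarily be under-reported. The definition does not say that; it leaves the outcome to investigator attribution.
- A reader might try to size the loss by assuming an irritation rate and multiplying by the share of subjects clear on Day 1. That models a rule under which only new-onset findings count, whereas Protocol 9.1 also counts aggravated ones. Both inputs would be invented.
- A reader might note "The vehicle (Placebo) lacks spinosad" and conclude that irritation from the vehicle would be hidden. It would not be: SAP 6.4.1 reports treatment-emergent events as numbers and percentages in each arm, so recorded vehicle irritation shows as an absolute rate.

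What the reply does not answer is that a separately named endpoint, examined on three days, reaches post-baseline tables only after an attribution judgement. A present/absent item can be counted by visit without a rating scale.

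**Conclusion.** The point holds as a gap in reporting. After baseline, skin irritation is tabulated only as adverse events, and the definition used allows irritation in infested skin to be classed as scabies. The plan also leaves unclear whether every observed irritation must be recorded as an adverse event.

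The size is unknown and cannot be derived from the documents. The conclusion rests on one assumption: that application irritation in infested skin can resemble scabies closely enough for attribution to be uncertain. The protocol's own description of the disease makes this plausible, but nothing in the documents shows how often it would occur. This is a worthwhile, inexpensive improvement to safety reporting; no efficacy inference depends on it.

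**What to change.** In SAP 6.4.2 and Protocol 8.5.4, add for the safety population:

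- the number and percent of subjects with skin irritation present on Days 1, 2 and 28/ET, by treatment group;
- a Day 1 to Day 2 shift by treatment group (absent to present, present to present, present to absent, absent to absent);
- both shown separately for subjects infested and not infested at baseline.

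In the same sections, state whether every observed skin irritation is recorded as an adverse event or only irritation that meets the Protocol 9.1 definition.

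Keep adverse event capture and severity grading. The shift table cannot show worsening within the present-to-present cell, so the two reports complement each other.

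The cost is SAP and protocol wording and one more descriptive table from data already collected, with no added visit, procedure or subject. There are two drawbacks: the reported irritation percentage may look less favourable than the adverse event rate, and some Day 2 irritation in infested subjects will be scabies itself. The split by baseline infestation helps the reader judge the second.
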